**Table 2 Secondary Objectives and Associated Endpoints**

Type	Objective	Endpoint
		
 
• BNP
 
• Laboratory assessments (hematology, clinical chemistry, and urinalysis)
 
• For subjects testing positive for COVID-19 during the intervention and follow-up periods, the number and proportion of subjects with AEs/SAEs, as well as the number and proportion of subjects with COVID-19 AEs/SAEs, and the proportion of asymptomatic subjects.
 

PK, Immunogenicity	To describe the PK and immunogenicity of MEDI3506 in subjects with DKD	MEDI3506 serum concentrations and ADA incidence occurring throughout the study
Efficacy	To evaluate the effect of MEDI3506 in combination with ACEi or ARB with and without dapagliflozin on albuminuria in subjects with DKD	
 
• Proportion of subjects with > 30% reduction in UACR at Day 169 (Week 24)
 
• Proportion of subjects with > 40% reduction in UACR at Day 169 (Week 24)
 
• Proportion of subjects with > 50% reduction in UACR at Day 169 (Week 24)
 
• Change from baseline to Day 85 (Week 12) in UACR
 
• Change from Day 85 (Week 12) to Day 169 (Week 24) in UACR
 

ACEi = angiotensin converting enzyme inhibitors; ADA = anti-drug antibody; AE(s) = adverse event(s); ARB = angiotensin receptor blockers; BNP = B-type natriuretic peptide; ECG = electrocardiogram; EOS = end of study; DBP = diastolic blood pressure; DKD = Diabetic Kidney Disease; LVEF = left ventricular ejection fraction; PK = pharmacokinetic; SAE(s) = serious adverse event(s); SBP = systolic blood pressure; TEAE(s) = treatment emergent adverse event(s); TESAE(s) = treatment emergent serious adverse event(s); UACR = urine albumin to creatinine ratio

CCI

CCI

CCI

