## 4.8.2 Sample Size

A sample size of 565 subjects randomized using a 95:95:95:140:140 ratio to receive either 30, 60 mg, 120 mg, or 300 mg MEDI3506 or placebo will give approximately 85:85:85:125:125 evaluable subjects per group. This will provide at least 85% power for the 300 mg arm and 80% power for the 30, 60, and 120 mg arms to detect a 30% reduction in change from baseline to Day 169 (Week 24) in UACR between each MEDI3506 treatment group and placebo group (or placebo/ MEDI3506 ratio of 1.429) with a one-sided alpha of 0.05 without multiplicity adjustment, assuming a coefficient of variation of 1.31 or standard deviation of 1.0 in log scale.

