## 4.8.3 Efficacy

### 4.8.3.1 Primary Efficacy Analysis

The primary efficacy endpoint for this study is change from baseline to Day 169 (Week 24) in UACR compared to placebo and will be analyzed based on the Per Protocol Population. For the intercurrent events, if a subject is lost to follow-up, discontinues treatment due to AE or lack of efficacy, or uses prohibited medication, the UACR data are treated as missing after the event and no imputation is performed. As UACR is assumed to follow a log-normal

distribution, it will be log-transformed for statistical analysis purposes. The primary analysis will use a mixed model repeated measures (MMRM) analysis of change from baseline in UACR without multiplicity adjustment. The model will adjust for fixed categorical effects of treatment, visit, and treatment-by-visit interaction, randomization stratification factors, and the continuous covariates of baseline log UACR and baseline log UACR-by-visit interaction. UACR will be log-transformed before entering the data in the MMRM analysis to alleviate the skewness of the data. Randomization stratification factors are with SGLT2i background or not, in Japan or rest of world.

To allow generality for the covariance structure for the repeated measures, the variance-covariance matrix will be assumed to be unstructured ie, purely data dependent. If the unstructured variance-covariance matrix will not fit, then suitable alternatives will be considered with details provided in the SAP. In this MMRM model, all subjects and all data points will be included. No subjects will be excluded because of missing data, and no imputation will be done for missing data. Additionally, there will be no adjustment for multiplicity.

Additionally, the primary efficacy endpoint will also be analyzed using an analysis of covariance adjusting for treatment, randomization stratification factors, and baseline log UACR with last-observation-carried-forward (LOCF) imputation for missing postbaseline measurements.

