#### **4.8.3.2 Secondary Efficacy Analysis**

The change from baseline to Day 85 (Week 12) in UACR will be analyzed similarly to that of the primary efficacy endpoint based on the Full Analysis Population. Change from Day 85 (Week 12) to Day 169 (Week 24) in UACR will be analyzed similarly to that of the primary efficacy endpoint based on the Per Protocol Population. For the proportions of patients with > 30%, > 40%, and > 50% reduction in UACR, logistic regression models will be used adjusting for treatment, randomization stratification factors, and baseline albuminuria status based on the Full Analysis Population and the Per Protocol Population.

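### The UACR responder models adjust for a baseline albuminuria status; continuous baseline log UACR, as in the primary model, would be a free but small improvement

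*Protocol*

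**What the plan says.** Protocol Table 2 lists five secondary efficacy endpoints. Three are the proportions of subjects with a UACR reduction above 30%, 40% and 50% at Day 169. For these, Section 4.8.3.2 states that "logistic regression models will be used adjusting for treatment, randomization stratification factors, and baseline albuminuria status based on the Full Analysis Population". It applies this to the Per Protocol Population too, and the Synopsis (Statistical Methods) repeats the model. The protocol does not give the levels of the status variable.

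The section before it, 4.8.3.1, analyses the same Day 169 change as the primary endpoint. Its MMRM includes "the continuous covariates of baseline log UACR and baseline log UACR-by-visit interaction". The supporting ANCOVA also adjusts for baseline log UACR.

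Inclusion criterion 3(c) admits a UACR of 100 to 3000 mg/g. Section 4.8.2 states power only for the continuous primary endpoint.

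**The concern.** Whether a subject shows a fall of more than 30% depends on where that subject starts, because high baseline values tend to regress towards the mean. Over a 30-fold eligible range, a category records that starting point coarsely. If the split is at 300 mg/g (an assumption), subjects at just over 300 and at 3000 mg/g receive the same adjustment. The plan already holds the finer measurement and uses it one section earlier.

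At stake is some precision in the four dose-against-placebo responder comparisons, and consistency between the primary and secondary models. No type I error or stated power figure is affected.

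**Working it through.** **1. The plan's own power.** Section 4.8.2 gives a 30% reduction (ln(1/0.7) = 0.3567), "assuming a coefficient of variation of 1.31 or standard deviation of 1.0 in log scale", one-sided alpha 0.05, and "approximately 85:85:85:125:125 evaluable subjects per group".

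Power = Phi(0.3567 / sqrt(1/n1 + 1/n0) - 1.645)

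- 85 v 125: 0.3567/0.1406 = 2.537, so Phi(0.892) = 81.4%.
- 125 v 125: 0.3567/0.1265 = 2.820, so Phi(1.175) = 88.0%.

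This agrees with the stated "at least 85% power for the 300 mg arm and 80% power for the 30, 60, and 120 mg arms".

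**2. What the cut alone costs.** Under the same log-normal model, the responder rate at cut c is Phi(ln(1-c) - m) on placebo and Phi(ln(1-c) - m + 0.3567) on active, where m is the mean log change on placebo. The protocol does not give m. All arms start dapagliflozin at Day 85, so m = 0 is only one case.

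Example: >30% cut, placebo median fall 20%. The rates are Phi(-0.134) = 0.447 and Phi(0.223) = 0.588. A one-sided two-proportion test then has 64.5% power (85 v 125) and 72.5% (125 v 125).

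Over the three cuts and placebo falls of 0 to 35%, power is 61 to 65% (85 v 125) and 69 to 73% (125 v 125). That is about 16 to 20 points below the full scale. This calculation has no baseline covariate in it, so the gap comes from the cut.

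**3. How much a status can hide.** Assume baseline is uniform on the log scale over 100 to 3000 mg/g, with SD ln(30)/sqrt(12) = 0.982. If follow-up has the same variance and the change has SD 1.0, the covariance of baseline and change is -0.5. The correlation is then -0.5/0.982 = -0.51. Take -0.5 as the strong case, a 20% placebo fall and the >30% cut:

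- Slope of change on log baseline: -0.5/0.982 = -0.509. Residual SD: sqrt(1 - 0.25) = 0.866. Mid-range baseline: sqrt(100 x 3000) = 548 mg/g.
- At 300 mg/g: mean change -0.223 + 0.509 x 0.602 = 0.083. Rate Phi((-0.357 - 0.083)/0.866) = 31%.
- At 3000 mg/g: mean change -0.223 - 0.509 x 1.701 = -1.089. Rate Phi((-0.357 + 1.089)/0.866) = 80%.

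At a correlation of -0.25 the same steps give 38% and 62%. At 0 the rates are equal.

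**4. What the covariate swap recovers.** Simulated power of the logistic model: 85 v 125, >30% cut, 20% placebo fall, 4,000 trials per setting, baseline as in step 3.

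| Baseline-change correlation | Status split at 300 mg/g | Continuous log UACR | Gain (points) |
|---|---|---|---|
| 0 | 65.0% | 65.0% | 0.0 |
| -0.25 | 65.5% | 66.0% | 0.5 |
| -0.5 | 68.8% | 70.8% | 2.0 |

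The 40% and 50% cuts behave similarly, which puts the gain at 2 to 3 points for -0.5. A separate run fitting both models to the same simulated trials gave about 0, 0 to 1 and about 2 points.

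A further simulation used a different baseline: log-normal around 500 mg/g with log SD 0.9, limited to 100 to 3000, residual SD 1.0, slopes 0, -0.2 and -0.4, and 1,500 trials per setting. The differences ran from -0.8 to +1.4 points, close to simulation error. Its strongest slope implies a correlation no stronger than -0.36/sqrt(1 + 0.36^2) = -0.34, so it is compatible with the table.

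**The case against.** The best case against the point is that it hardly matters. These are unpowered secondary endpoints, and the gain is 0 to 3 points. The upper end needs a correlation the protocol does not give, and the 300 mg/g split is not in the protocol either. A secondary model with a different covariate from the primary model is not a contradiction. The definition of the status can properly be left to the SAP, which was not at hand. The responder outcome is itself computed from each subject's continuous baseline, so that value is not discarded altogether. All of this stands, and it limits the point to an optional improvement. It gives no reason to prefer the status term, though: a SAP can define its levels, but the protocol has already chosen the coarser form of a variable it holds in full.

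A reader might go further and infer that three of the five secondary efficacy endpoints waste 16 to 20 points of power, and that the categorical baseline shares the blame. The documents do not support this. The full-scale Day 169 comparison is the primary endpoint, with continuous baseline and its own power statement. No power is claimed for the proportions, and the visible text rests no decision on them. They answer a different question: how many subjects reach a given reduction. The baseline coding contributes almost nothing to the gap. Nor would deriving the proportions from the fitted MMRM be a remedy, since that only re-expresses the primary result under log-normality.

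**Conclusion.** The point holds as a minor, cost-free improvement. The responder models name a baseline term that is naturally read as a category, where a continuous one is available and already used. Replacing it is worth about 0 to 2-3 points of power for 85 v 125. That range rests on four assumptions: a baseline-change correlation between 0 and -0.5, a status split at 300 mg/g, the plan's log SD of 1.0, and a placebo fall of 20%. The counts are the plan's evaluable numbers. The Full Analysis Population may be larger, so these figures illustrate the size of the effect and are not power for that analysis as written. A finer status variable would make the gain smaller still. No figure stated in the protocol is wrong.

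**What to change.** In Section 4.8.3.2 and in the Synopsis (Statistical Methods), replace the baseline albuminuria status term in the three responder logistic models with continuous baseline log UACR, and carry this into the SAP. Keep the three endpoints, their cuts and both analysis populations as they are.

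The cost is one phrase in two places. No new data, visits or sample size are needed. The continuous term assumes an approximately linear relation between log UACR and the log odds of response, much as the primary model assumes linearity in log UACR for the mean change.

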#### **4.8.3.3 Exploratory Analyses**

Exploratory endpoints will be summarized by treatment group based on the Full Analysis Population and/or the Per Protocol Population.

Additional details of the exploratory endpoint analyses will be described in the SAP.

#### **4.8.3.4 Subgroup Analyses**

Subgroup analyses may be performed and will be described in the SAP as required.

#### **4.8.3.5 Sensitivity Analysis**

Sensitivity analyses will be performed to assess the potential impact on study endpoints due to COVID-19. Other sensitivity analyses may also be performed. Details will be described in the SAP.

#### **4.8.4 Safety**

##### **4.8.4.1 Analysis of Adverse Events**

Safety analysis will be based on the Safety Analysis Population. AE collection will begin after the subject signs the ICF and lasts until the end of the study. AEs will be coded using the Medical Dictionary for Regulatory Activities (MedDRA) by system organ class (SOC) and preferred term (PT). Specific AEs will be counted once for each subject for calculating rates, but will be presented in total in subject listings. In addition, if the same AE occurs multiple times within a particular subject, the highest severity and level of causality will be reported. All TEAEs will be summarized overall and by MedDRA SOC and PT, by severity and relationship to investigational product. All TEAEs related to dapagliflozin will also be summarized. In addition, summaries of deaths, SAEs and treatment discontinuations due to AEs will be provided. Injection-site reactions will be presented. For subjects testing positive for COVID-19, the number and proportion of subjects with COVID-19 AEs and SAEs and the proportion asymptomatic subjects will be summarized. Number of subjects seropositive for SARS-CoV-2 at end of study who were seronegative at randomization visit will also be summarized.

##### **4.8.4.2 Analysis of Clinical Laboratory Parameters**

Clinical laboratory safety tests including serum chemistry and hematology parameters will be summarized using descriptive statistics at each time point by treatment group. Change from baseline to each post baseline time point in these data will also be summarized, where appropriate. A shift table will be provided for these clinical laboratory parameters as well, where possible.

##### **4.8.4.3 Analysis of Vital Signs and ECGs**

Vital sign results and ECGs will be summarized using descriptive statistics at each time point by treatment group.

##### **4.8.4.4 Other Safety Endpoints**

Other safety endpoints, such as left ventricular ejection fraction (LVEF) as measured by echocardiogram and BNP, will be summarized using descriptive statistics at each time point by treatment group.

#### **4.8.5 Analysis of Immunogenicity/Pharmacokinetics**

The incidence rate of positive antibodies to MEDI3506 and ADA titer will be reported by treatment group. Samples may be utilized for further characterization of the ADA response,

including possible assessment of nAbs. If there is a high incidence of ADAs, the association of ADA with MEDI3506 concentration will be assessed. In addition, the relationship between ADA and PD, efficacy, and safety parameters may be evaluated.

MEDI3506 serum PK concentrations and descriptive statistics will be tabulated per dose group. Additional PK analyses may be conducted as appropriate. If the data allow, population PK analysis will be performed but will not be reported in the CSR.

As an exploratory analysis, dapagliflozin plasma concentrations will be summarized by descriptive statistics for each visit and each sample point for dapagliflozin-treated subjects by dose cohort. Further details of this will be provided in the SAP. Additional PK analyses may be conducted as appropriate. If the data allow, population PK analysis will be performed, but will not be reported in the CSR.

#### **4.8.6 Data and Safety Monitoring Board**

An independent DSMB will be formed to evaluate safety data from concurrently conducted MEDI3506 Phase 2 clinical studies in other indications. Unblinded review of safety data will be required for indications where the potential risks of MEDI3506 are high due to the disease under study (DUS) and the common comorbidities of particular subject populations. Safety data from this study will be provided to the DSMB in order to perform the oversight of all safety data.

The DSMB will be responsible for safeguarding the interests of the subjects in the study by assessing the safety of the intervention during the trial and for reviewing the overall conduct of the study. The DSMB will be composed of independent experts and will conduct safety reviews on a scheduled and, if needed, ad hoc basis. The DSMB will have access to data aggregated by treatment group and will be able to review collected study data by treatment while the study is ongoing. The DSMB will review prespecified data periodically to ensure subject safety and make recommendations to the sponsor regarding further conduct of the study. A separate charter will detail the rules, meeting frequency and scope of the responsibilities of the DSMB.

CCI

## **5 ASSESSMENT OF SAFETY**

### **5.1 Definition of Adverse Events**

An AE is the development of any untoward medical occurrence in a subject or clinical study subject administered a medicinal product and which does not necessarily have a causal relationship with this treatment. An AE can therefore be any unfavorable and unintended sign (eg, an abnormal laboratory finding), symptom (eg, nausea, chest pain), or disease temporally associated with the use of a medicinal product, whether or not considered related to the medicinal product.

The term AE is used to include both serious and non-serious AEs and can include a deterioration of a pre-existing medical occurrence. An AE may occur at any time, including run-in or washout periods, even if no study treatment has been administered.

Elective treatment or surgery or preplanned treatment or surgery (that was scheduled prior to the subject being enrolled into the study) for a documented pre-existing condition that did not worsen from baseline is not considered an AE (serious or nonserious). An untoward medical event occurring during the prescheduled elective procedure or routinely scheduled treatment should be recorded as an AE or SAE.

### **5.2 Definition of Serious Adverse Events**

An SAE is any AE that:

- Results in death
- Is immediately life-threatening
- Requires inpatient hospitalization or prolongation of existing hospitalization
- Results in persistent or significant disability/incapacity
- Is a congenital anomaly/birth defect in offspring of the subject
- Is an important medical event that may jeopardize the subject or may require medical intervention to prevent one of the outcomes listed above

Medical or scientific judgment should be exercised in deciding whether expedited reporting is appropriate in this situation. Examples of medically important events are intensive treatment in an emergency room or at home for allergic bronchospasm, blood dyscrasias, or convulsions that do not result in hospitalizations; or development of drug dependency or drug abuse.

### **5.3 Definition of Adverse Events of Special Interest**

An adverse event of special interest (AESI) is one of scientific and medical interest specific to understanding of MEDI3506 and may require close monitoring and rapid communication by the investigator to AstraZeneca. An AESI may be serious or non-serious. The rapid reporting

of AESIs allows ongoing surveillance of these events in order to characterize and understand them in association with the use of this investigational product.

The following AESIs will be particularly monitored in this study (see the Safety Handling Plan for instructions and timing on completing any additional information required for specific types of events related to the categories noted below):

- Serious hypersensitivity (including Type 1 to 4 hypersensitivity reactions), for example anaphylaxis (see also Appendix B) and severe allergic reactions, and immune complex disease.
- Injection-site reactions.
- Heart failure.
- Serious infections (including opportunistic infections and viral reactivations), for example varicella zoster/herpes simplex virus, Epstein Barr virus/cytomegalovirus, and TB.
- Gastrointestinal adverse events.

## **5.4 Recording of Adverse Events**

AEs will be recorded on the eCRF using a recognized medical term or diagnosis that accurately reflects the event. AEs will be assessed by the investigator for severity, relationship to the investigational product, possible etiologies, and whether the event meets criteria of an SAE and therefore requires immediate notification to AstraZeneca (see Section 5.5). See Section 5.2 for the definition of SAEs and Appendix A for guidelines for assessment of severity and relationship.

If an AE evolves into a condition that meets the regulatory definition of “serious”, it will be reported on the SAE Report Form.

### **5.4.1 Time Period for Collection of Adverse Events**

AEs will be collected from time of signature of informed consent throughout the treatment period and including the follow-up period at Visit 10 or to date of last contact.

All SAEs will be recorded from the time of informed consent.

### **5.4.2 Follow-up of Unresolved Adverse Events**

Any AEs that are unresolved at the subject’s last AE assessment or other assessment/visit as appropriate in the study are followed up by the investigator for as long as medically indicated, but without further recording in the eCRF. AstraZeneca retains the right to request additional information for any subject with ongoing AE(s)/SAE(s) at the end of the study, if judged necessary.

### 5.4.3 Deaths

All deaths that occur during the study, including the protocol-defined follow-up period must be reported as follows:

- Death clearly the result of disease progression should be reported and documented in the eCRF but should not be reported as an SAE.
- Where death is not due (or not clearly due) to disease progression, the AE causing the death must be reported as an SAE within 24 hours. The report should contain a comment regarding the co-involvement of disease progression, if appropriate, and should assign main and contributory causes of death.

Deaths with an unknown cause should always be reported as an SAE. A post-mortem (autopsy) may be helpful in the assessment of the cause of death, and if performed a copy of the post-mortem results should be forwarded to AstraZeneca representative(s) within the usual timeframes (refer to Section 5.5 for additional information).

### 5.4.4 Adverse Events Based on Signs and Symptoms

All AEs spontaneously reported by the subject or reported in response to the open question from the study site staff: *'Have you had any health problems since the previous visit/you were last asked?'*, or revealed by observation will be collected and recorded in the eCRF. When collecting AEs, the recording of diagnoses is preferred (when possible) to recording a list of signs and symptoms. However, if a diagnosis is known and there are other signs or symptoms that are not generally part of the diagnosis, the diagnosis and each sign or symptom will be recorded separately.

